5.3 Prohibited Medications

The following treatments are prohibited while on the compassionate study protocol:

- Any other anti-lymphoma therapy (e.g. radiation therapy, hormonal therapy for cancer,

cancer immunotherapy or other biologic therapy).

- Herbal medications are not allowed throughout the trial. Patients should stop using these herbal medications at least 7 days prior to C1D1.
- **Strong inhibitors or inducers of CYP3A4** including grapefruit products, herbal medication. Patients should stop using these medications at least 7 days prior to C1D1.
- **Strong inhibitors or inducers of CYP2C9** including herbal medications. Patients should stop using these medications at least 7 days prior to C1D1.
- **Substrates of CYP3A4 enzyme with a narrow therapeutic range** (e.g. Warfarin and phenytoin). Patients should stop using these medications at least 7 days prior to C1D1.
- Steroids > 20 mg unless for management of toxicity.

Discontinuation of patient who received concomitant/prohibited medication will be taken by the PI in consultation with medical monitor on case by case basis, after reviewing ongoing clinical benefit and risk. The decision to allow a patient to continue will be documented.

5.4 Procedures for Monitoring Subject Compliance.

The following measures will be employed to ensure treatment compliance. Subjects will be asked to bring any unused study drug to the study center at their next visit. Site personnel will count and record the number of used and unused study drug tablets at each visit. The study coordinator will question the patient regarding adherence to the dosing regimen, record the number of tablets and strengths returned, the date returned and determine treatment compliance before dispensing new medication to patient.

6 TRIAL ASSESSMENT AND PROCEDURE

6.1 Overview

The Schedule of Events (**Table 1**) summarizes the trial procedures to be performed at each visit and is divided into following:

1. Screening (Day -14 to Day C1D1)
2. On treatment procedures (C1D1 to EOT)
3. End of Treatment (EOT)
4. End of Study (EOS) (Day +30 from last dose)

6.2 Screening Procedure

6.2.1 Informed Consent

The investigator/qualified designee must obtain written informed consent from each potential subject or each subject's legally acceptable representative prior to participating in a clinical trial. Consent must be documented by the subject's dated signature or by the subject's legally acceptable representative's dated signature on an IRB/IEC approved consent form along with the dated signature of the person conducting the consent discussion. A copy of the signed and dated consent form should be given to the subject before participation in the trial.

The initial informed consent form, any subsequent revised written informed consent form and any written information provided to the subject must receive the IRB/IEC's approval/favorable opinion in advance of use. The subject or his/her legally acceptable representative should be informed in a timely manner if new information becomes available that may be relevant to the subject's willingness to continue participation in the trial. The communication of this information will be provided and documented via a revised consent form or addendum to the original consent form that captures the subject's dated signature or by the subject's legally acceptable representative's dated signature.

6.2.2 Enrollment of patient

During the screening period, the investigator/designee will complete the patient enrollment form and submit to the Sponsor for review and approval prior to enrolling the patient in the study.

6.2.3 Screening Procedure

Medical history, ECOG status and weight will be taken. Information on prior medication use, prior therapies including Tenalisib treatment will also be obtained to confirm eligibility of the patient.

6.3 Treatment and Study Procedures

Patients will visit the study center every three months until documented disease progression or treatment discontinuation due to toxicity or consent withdrawal. During these visits, Tenalisib will be dispensed and medication compliance will be monitored. Safety and efficacy assessments will be done as mentioned below.

- Safety assessments:**

- Safety assessment will be done during the visits and AEs will be reported as required by the protocol.
- Concomitant medications may be administered as clinically indicated.
- A medication history should be reviewed at each clinic visit to assure no potential adverse events are noted.
- There are no specific safety labs or evaluations (including vitals, physical examinations, pregnancy tests and ECGs) required as per protocol. As part of SOC, laboratory tests or other evaluations can be done per Investigator's discretion. Adverse events (AEs, SAEs and deaths) will be recorded and reported for 30 calendar days after last dose or until a new anti-cancer treatment is initiated, whichever is earlier. After this period, only AEs, SAEs, or deaths assessed by the investigator as treatment related are to be reported.

- Efficacy assessments:**

- Disease assessments [e.g. radiological imaging (e.g. CT, PET-CT) or any other appropriate evaluation tool (e.g. mSWAT in case of skin involvement)] should be performed as part of SOC. These evaluations (e.g. measurement of lymph node, mSWAT) will not be recorded in the CRF, however, date of disease progression will be reported .

- Drug dispensing:**

- Patients will be given drug supply for 3 months.

Table 1: Schedule of Events

	Screening and Eligibility	Cycle 1	Cycle 4	Cycle 7 Through EOT	EOT	EOS ¹¹
Day	D-14 to D1	D1	D1	D1	-	-
Window period	-14	-	±7	±7	-	+30
Study Days	D-14 to D1	1 ¹	85	169	-	-
Informed Consent	X	-	-	-	-	-
Eligibility Confirmation	X	-	-	-	-	-
Demographics ²	X	-	-	-	-	-
Medical history ³	X	-	-	-	-	-
Vitals	-	SOC*	SOC*	SOC*	SOC*	-
Weight ⁴	X	SOC*	SOC*	SOC*	SOC*	-
Physical exam	-	SOC*	SOC*	SOC*	SOC*	-
ECOG Performance	X	SOC*	SOC*	SOC*	SOC*	-
Complete blood count	-	SOC*	SOC*	SOC*	SOC*	-
Chemistry	-	SOC*	SOC*	SOC*	SOC*	-
PT/INR	-	SOC*	SOC*	SOC*	SOC*	-
Urinalysis (routine)	-	SOC*	SOC*	SOC*	SOC*	-
Pregnancy test ⁴	-	SOC*	SOC*	SOC*	SOC*	-
12-lead ECGs	-	SOC*	SOC*	SOC*	SOC*	-
Disease assessment ⁵	-	SOC*	SOC*	SOC*	SOC*	-
Date of discontinuation ⁶	-	-	-	-	X	-
Drug Dispensing ⁷	-	X	X	X	-	-
Tenalisib treatment ⁸	-	X	X	X	-	-
Drug compliance	-	-	X	X	X	-
AE evaluation ⁹	X	X	X	X	X	X
SAE evaluation ¹⁰	X	X	X	X	X	X
Concomitant medication	X	X	X	X	X	X

Note: *There are no specific safety labs or evaluations (including vitals, physical examinations, pregnancy tests, ECGs and radiological evaluation/mSWAT scoring) required as per protocol. As part Standard of care (SOC), laboratory tests or any evaluations can be done per Investigator's discretion.

Foot notes:

1. Depending on the feasibility, screening/eligibility assessment and dispensing of the study drug can be done on same day. Assessment performed in previous study (e.g. Medical history, vital signs demographics, Weigh and ECOG) can be used for eligibility evaluation. The first day of Tenalisib administration will be considered as C1D1
2. Demographic profile will include age, sex and race.
3. Medical history will include history of cancer, past history of Tenalisib, no of prior therapies and prior medication (last 4 weeks); and other medical history. Any medical significant history at subsequent visit will be captured as adverse event.
4. Applicable only for women of child-bearing potential.
5. Disease assessment may include evaluation of disease condition by radiological imaging (e.g. CT, PET, PET-CT or MRI) or by any other appropriate evaluation tool depending on the disease condition (e.g. mSWAT in case of skin involvement, bone marrow biopsy in case of marrow involvement). Disease evaluation will be performed at the discretion of study investigator.
6. The day of the last dose of study drug will be considered as EOT.
7. Tenalisib will be dispensed in a HDPE container having 30 tablets of Tenalisib. A 3-month supply of study drug will be dispensed at each visit. In case of roll over from the combination study, the combination agent (e.g.

romidepsin) will be administered as part of SOC and will not be supplied/provided by Rhizen Pharmaceuticals S.A.

8. Patients showing clinical benefit (have achieved either SD, PR or CR) will continue to receive Tenalisib as they are currently receiving in previous protocols. The treatment plan will be the same dosing schedule unless dose adjustments or delays are necessary for toxicity management.
In case of roll over from a combination study, the investigator has a choice to continue with the combination therapy or to maintain the patient on Tenalisib monotherapy. If combination agent is continued, it will be administered as a part of SOC.
9. All AEs should be recorded spanning from the informed consent drug until 30 calendar days after the last dose of study drug or till new anti-cancer treatment is initiated whichever is earlier.
10. All events that meet the definition of serious but, in the opinion of the treating investigator, are clearly expected from the Patient's disease or related to disease progression (i.e. there exists no reasonable possibility that they were caused by the study drug) should be reported on the case report forms and do not require expedited reporting. In addition, progression of malignancy (including fatal outcomes), if documented by use of appropriate method (e.g. CT/ PET) or clinically confirmed, should not be reported as a serious adverse event.
11. Patients should be followed for AEs for 30 calendar days after the last dose of study treatment or till new anti-cancer treatment is initiated whichever is earlier. Telephonic follow up during this period is acceptable. All new AEs occurring during this period should be reported and followed until resolution unless, in the opinion of the investigator, the adverse event or laboratory abnormality/ies are not likely to improve because of the underlying disease.

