3.4.3 Preparation and administration of Investigational Products

At each visit, patients will be dispensed sufficient quantity of Tenalisib until the next visit. Study drug compliance will be reviewed with the patient at the beginning of cycle. Study drug compliance will be documented, including missed doses.

Guidelines for administration of Tenalisib:

- Method of administration: Tenalisib will be administered orally twice daily
- Pre-medications: None. No routine prophylactic anti-emetics or pre-medications will be given outside of protocol requirements. However, these medications may be administered for treatment of symptoms/adverse events.
- Tenalisib tablets will be self-administered orally twice daily one hour before a major meal (e.g. breakfast and dinner). Patients should not consume food during this one-hour period. ***Please note, patients will continue to receive the same dose they were receiving in previous protocols. (e.g. If patient is receiving Tenalisib 400 mg BID while rolling over, he/she will continue to receive 400 mg BID dose in compassionate study protocol).***
- Tenalisib tablets should be taken at approximately same time each day. Tablets should be swallowed; and should NOT be crushed or chewed.
- If a dose of Tenalisib is missed, it should be taken as soon as possible on same day with an interval of 8 hrs between two doses. If it is missed for the entire day, it should not be repeated. If vomiting occurs, no attempt should be made to replace the vomited dose.
- Study drug compliance should be reviewed with the patient at the beginning of cycle. Missed doses should be documented.

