4 SELECTION AND WITHDRAWAL OF SUBJECTS

4.1 Inclusion Criteria

Patients must meet all inclusion criteria to be eligible for participation in this study:

1. Patients must be currently receiving treatment with Tenalisib either as monotherapy or in combination with another agent on a previously approved protocol for hematological malignancies including but not limited to indications DLBCL, iNHL, PTCL, CTCL, CLL and HL.
2. Patients must have had at least one efficacy evaluation following the initiation of Tenalisib in previous study and should have achieved either SD, PR or CR.
3. Patients must have completed at least 6 cycles of Tenalisib in previous study
4. Ability to swallow and retain oral medication.
5. Female patients of child-bearing potential must consent to use two medically acceptable methods of contraception throughout the study period and for 4 weeks after the last dose of Tenalisib. A barrier method of contraception must be included.
6. Male patients must be willing to use adequate contraceptive measures throughout the study period and for 12 weeks after the last dose of Tenalisib.
7. Willingness and ability to comply with trial and follow-up procedures.
8. Willingness to provide new written informed consent.

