4.2 Exclusion Criteria

Patients must meet none of the following exclusion criteria to be eligible for participation in this study:

1. Patient has been discontinued from their previous Tenalisib study 4 weeks prior to entering the compassionate use trial.
2. Patient progressed while receiving Tenalisib therapy in his/her previous study.
3. Pregnant or lactating woman.
4. Inability or unwillingness to comply with study and/or follow-up procedures outlined in the protocol.
5. Concurrent condition that in the investigator's opinion would jeopardize compliance with the protocol.

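### Pregnancy is an exclusion, but no pregnancy test is required before a 3-month supply is dispensed; secondarily, the baseline used in the dose tables is undefined for rolled-over patients

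*Combined protocol and SAP*

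**What the plan says.** Exclusion 3 in protocol section 4.2 reads "Pregnant or lactating woman" and names no means of checking. Section 6.2.3 sets out the screening work: "Medical history, ECOG status and weight will be taken", plus prior medication and prior therapies. In Table 1 the pregnancy-test row has a dash at screening and a standard-of-care (SOC) marker from Cycle 1 to EOT. The note that explains the marker says "There are no specific safety labs or evaluations (including vitals, physical examinations, pregnancy tests, ECGs and radiological evaluation/mSWAT scoring) required as per protocol" and leaves testing to the investigator.

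Footnote 1 to Table 1 says that, where feasible, "screening/eligibility assessment and dispensing of the study drug can be done on same day". It also lets assessments from the previous study serve for eligibility. Under drug dispensing, section 6.3 says "Patients will be given drug supply for 3 months".

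The plan does contain safeguards. Inclusion 5 says "Female patients of child-bearing potential must consent to use two medically acceptable methods of contraception throughout the study period", and a barrier method must be one of them. Section 7.4.1 asks women to report a missed or late period and requires drug to be withheld pending a test once pregnancy is suspected on treatment. Section 6.2.2 sends an enrolment form to the sponsor for approval.

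On dosing, several rules in section 7.5 and Tables 2 and 3 turn on a *baseline* value, or on a count *before therapy*. Neither the protocol nor the SAP says which time point is meant.

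**The concern.** An eligibility criterion is only as good as the step that verifies it. Here a woman with an early, unrecognised pregnancy could be enrolled and given a further three months of drug with every protocol step followed. The protocol treats pregnancy on drug as grave: section 7.4.1 requires immediate and permanent discontinuation once it is confirmed, and section 3.4.5 says that reproductive toxicity and genotoxicity data are absent. Lactation can be established by asking; early pregnancy may not be.

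The baseline question is a lesser, related matter. Patients enter after at least 6 cycles of Tenalisib (inclusion 3), so the value before the parent study and the value at entry can differ. If investigators choose differently, the same laboratory result can lead to different dose actions.

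**Working it through.** **Pregnancy: does any step yield a result before dispensing?**

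- Section 4.2, exclusion 3: criterion stated, no method.
- Section 6.2.3 and the Table 1 screening column: no pregnancy test.
- Table 1, Cycle 1 Day 1: SOC only, so optional.
- Section 7.4.1: a test is called for on suspicion in a woman already receiving drug, which is too late to verify entry.
- Section 6.2.2: sponsor approval of a form; no test result is specified for it.
- Footnote 1: parent-study assessments may be reused. The list of examples is open but does not mention a pregnancy test, and no age limit is set.

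No step requires a dated result before the first supply is handed out.

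**Time to the next scheduled visit.** Table 1 puts C1D1 at study day 1 and Cycle 4 Day 1 at study day 85, with a window of ±7 days. Section 3.4.3 gives the frequency: "Tenalisib will be administered orally twice daily".

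- Interval: 85 − 1 = 84 days; 84 − 7 = 77 and 84 + 7 = 91.
- Doses: 84 × 2 = 168; 77 × 2 = 154; 91 × 2 = 182.

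These figures apply if no SOC test or missed-period report intervenes and no dose is missed.

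**Tests the fix would add.** The synopsis plans about 50 patients. The share of women of child-bearing potential is not given. Assuming 5% to 20%: 0.05 × 50 = 2.5, rounded up to 3; 0.20 × 50 = 10.

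**Baseline: can the two readings disagree?** Table 3 gives these ALT/AST rows:

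- Grade 1-2: above 1 to 3 × ULN, or 1.5 to 3 × an abnormal baseline. Keep the dose and start prednisone.
- Grade 3: above 5 to 20 × ULN or × an abnormal baseline. Withhold.
- Grade 4: above 20 × ULN or × an abnormal baseline. Stop permanently.

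Take an on-study ALT of 6 × ULN and a normal pre-treatment ALT (both assumed). On the pre-treatment reading, 6 > 5, so Grade 3: withhold. On the entry reading, with assumed entry values:

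| Entry ALT | Ratio | Row |
|---|---|---|
| 3 × ULN | 6 / 3 = 2.0 | Grade 1-2: keep dose, prednisone |
| 2 × ULN | 6 / 2 = 3.0 | on the upper limit of Grade 1-2 |
| 1.5 × ULN | 6 / 1.5 = 4.0 | no row |

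Only the first line is a clean conflict. The second sits on the boundary. The third reflects a gap between 3 × and 5 × that exists on either reading: 4 × ULN with a normal baseline has no row either. The permanent-stop limit is 20 × ULN on the pre-treatment reading, against 20 × 1.5 = 30, 20 × 2 = 40 or 20 × 3 = 60 × ULN on the entry reading.

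**Would the pre-treatment value suit every row?** No. Table 2 says not to modify the dose if Grade 4 thrombocytopenia was there at baseline. It gives a similar exemption in the febrile neutropenia row when the ANC was below 1 × 10⁹/L before therapy and is still above 0.5 × 10⁹/L. A patient who started the parent study with such a count and then recovered would keep the exemption when a new, drug-related fall occurred. The liver and QTcF rows favour the pre-treatment value; the cytopenia exemptions need the situation at entry.

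**The case against.** The strongest reply is that light monitoring is deliberate. The no-required-tests rule appears in the synopsis, in section 6.3 and under Table 1, and the purpose in section 9 is continued access. Entry is not first exposure: these women come from a parent trial, and a recent pregnancy test may well exist there. Footnote 1 would allow its use. This stands as a reason to keep the design light. It does not stand as verification, because nothing requires that result to exist, to be recent or to be recorded.

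A reader might infer that the plan leaves patients without laboratory surveillance. The documents do not support that. Section 3.4.5 recommends monitoring of liver enzymes and thyroid function, says patients should be watched for raised ALT/AST and neutropenia, and calls for interruption at Grade 3 or higher. Tables 2 and 3 ask for weekly or twice-weekly checks once certain toxicities are known.

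A reader might also infer that the Grade 3/4 incidence is biased downwards because testing is optional. The frequency of SOC testing is not given, and footnote 3 to Table 1 pulls the other way by turning significant history found at a later visit into an adverse event. Neither direction nor size can be established.

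On baseline, section 7.5 makes the tables guidance under the investigator's judgement. The Grade 1-2 transaminase row itself says to withhold if Grade 2 develops, or Grade 1 worsens, while on steroids. Both points soften the conflict shown above. They leave the term undefined.

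**Conclusion.** The pregnancy point holds on the text: exclusion 3 can be signed off without a result, on the day a 3-month supply is dispensed. How many women could be affected cannot be computed, because neither the number of women of child-bearing potential nor the frequency of SOC testing is given. For one such woman the unscreened interval to the next scheduled visit is 84 days (77 to 91), or 168 doses (154 to 182), on the conditions stated. It would go too far to say that pregnant women will be treated; the contraception rules, missed-period reporting, optional testing and sponsor review all make it less likely. This is a cheap, safety-relevant improvement that should be made.

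The baseline point is secondary. The ambiguity is real, but a clear reversal of action appears at only one of the three assumed entry values, and the tables are advisory. The documents do not support one pre-treatment definition for all rows.

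**What to change.** 1. Amend Table 1 and footnote 1: for women of child-bearing potential, a negative pregnancy test dated within the 14-day screening window is recorded before C1D1 dispensing. A parent-study result within that window is accepted; otherwise one test is done at screening. Cost: at most one simple test per such woman, or 3 to 10 tests in all under the assumed 5% to 20% share. Same-day dispensing remains possible once the result is available. This does not address conception after entry, which still rests on contraception, missed-period reporting and SOC testing.

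2. In section 7.5, define the reference value row by row. For ALT/AST, bilirubin and QTcF, use the parent-study pre-treatment value, carried over with its date, so that elevations on drug do not loosen the thresholds. For the pre-existing-cytopenia exemptions in Table 2, apply them only if the cytopenia is still present at entry. Cost: a few sentences and carry-over of dated values from the same sponsor's parent trials, assuming they were recorded. Because Table 1 requires no blood count at entry, a patient claimed for the exemption would need a recent parent-study or SOC count. One trade-off remains: a patient whose pre-treatment liver values were abnormal and have since recovered keeps the more lenient limit, although the investigator may act earlier.

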7 ASSESSMENT OF SAFETY

7.1 Adverse Events

7.1.1 Definitions of adverse events

Any untoward medical occurrence in a patient or clinical investigation subject administered a pharmaceutical product and which does not necessarily have a causal relationship with this treatment.

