7.2 Adverse Event/Serious Adverse Event Causality Assessment

The causality assessment will be categorized as related and not related.

- **Related:** All toxicities should be considered to be related to Tenalisib unless there is a clear alternative explanation.
- **Not related:** If there is no temporal association, or another etiology has been identified as the cause, or the trial treatment cannot be implicated based upon the current information.

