3.3 Protocol-Defined Events of Special Interest

The following are events of special interest and will need to be reported expeditiously.

- Pregnancy, Abortion, Birth Defects/Congenital Anomalies

Congenital anomalies/birth defects always meet SAE criteria, and should therefore be expeditiously reported as an SAE, using the previously described process for SAE reporting. A Pregnancy Form should also have been previously completed and will need to be updated to reflect the outcome of the pregnancy.

- Overdose

An overdose is defined as accidental or intentional administration of any dose of product that is considered both excessive and medically important. For purposes of this trial, an overdose will be defined as any dose exceeding the proposed dose of Tenalisib (e.g. > 800 mg twice a day).

The safety endpoints will include:

- Incidence of AEs and related AEs
- Incidence of grade 3, grade 4 and grade 5 AEs
- Incidence of SAEs and deaths

The analyses of safety will be based on the frequency of adverse events for patients who received at least one dose of study treatment.

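### Table 1 footnote 3 records late-noted medical history as an adverse event with no onset or worsening condition, so pre-existing or carried-over conditions can enter the AE counts

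*Combined protocol and SAP*

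**What the plan says.** Table 1 schedules medical history at screening only, while AE evaluation is scheduled at every visit from screening to end of study. Footnote 3 defines the history as covering the cancer history and "past history of Tenalisib, no of prior therapies and prior medication (last 4 weeks); and other medical history". It then gives the rule for anything found later: "Any medical significant history at subsequent visit will be captured as adverse event".

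The surrounding text is as follows.

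- Section 6.2.3 requires a history for this study: "Medical history, ECOG status and weight will be taken".
- Table 1 footnote 1 allows parent-study data to be reused: "Assessment performed in previous study (e.g. Medical history, vital signs demographics, Weigh and ECOG) can be used for eligibility evaluation".
- Table 1 footnote 9 gives the recording window: "All AEs should be recorded spanning from the informed consent drug until 30 calendar days after the last dose of study drug". The window closes sooner for a patient who starts another cancer therapy.
- Section 7.1.1 defines an AE broadly: "Any untoward medical occurrence in a patient or clinical investigation subject administered a pharmaceutical product", whether or not the treatment caused it. It says nothing about conditions already present.
- The safety endpoints at the end of SAP Section 3.3 begin with "Incidence of AEs and related AEs". They are summarised as AE frequencies in patients who took at least one dose.

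**The concern.** A recording rule for a rollover study has to separate what began in this study from what patients brought with them. Every entrant is already taking Tenalisib and has completed six or more cycles (inclusion criteria 1 and 3), so some may arrive with an ongoing toxicity or another condition acquired in the parent trial. If such a condition is missed at screening and first mentioned at Cycle 4 or later, footnote 3 as written makes it an AE here.

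What is at stake is the AE summary. With no control arm, nothing cancels the error. An entry of this kind adds to the count for its own term and grade, and may add to overall incidence. Two sites could also record the same late-reported condition differently, depending on how each reads the footnote.

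**Working it through.** The plan states no expected AE rate or other figure on this point, so there is nothing to reproduce. The check is a comparison of texts, followed by simple arithmetic on scale.

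**Following one case through the documents.** Take a patient whose condition began during the parent trial, was not listed at screening, and is first noted at the Cycle 4 visit.

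1. *Table 1.* History is closed after screening, so no later visit has a scheduled place for it other than AE evaluation.
2. *Footnote 3.* The condition is medically significant history at a subsequent visit, so it is captured as an AE. No onset date, newness or worsening is asked for.
3. *Footnote 9.* Recording starts at consent. The footnote does not say whether the onset date or the date of first mention must fall in the window, so it does not clearly override footnote 3.
4. *Sections 7.1.1 and 7.1.2.* The definition does not exclude a pre-existing condition. The word new is applied to AEs only in the post-treatment follow-up period (Section 7.1.2, Table 1 footnote 11).
5. *SAP Sections 3.1 and 3.3.* The protocol text is repeated. There is no treatment-emergent definition, baseline rule, or rule for parent-study AEs still ongoing at rollover. The entry is counted.

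The baseline against which a site could check is thin. At screening Table 1 requires history, weight and ECOG status, but no vital signs, physical examination, blood count or chemistry, and footnote 1 allows screening and dispensing on the same day.

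**Scale.** The synopsis gives N of about 50.

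- One misclassified patient adds 1/N = 1/50 = 2.0 percentage points to the incidence of that event term.
- For overall incidence, let p be the true share of patients with at least one on-study AE, and q the share of the remaining patients whose only recorded AE is a pre-existing condition. Then observed incidence = p + (1 − p)q, and the excess is (1 − p)q.
- Neither p nor q is in the documents. Purely to show how the formula behaves, assume p from 30% to 90% and q from 2% to 20%. The excess runs from (1 − 0.90) × 0.02 = 0.002, or 0.2 points, to (1 − 0.30) × 0.20 = 0.14, or 14 points.
- As p approaches 100%, overall incidence hardly moves. The error then falls on event counts and individual terms.

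This range shows the dependence on p and q. It is not an estimate for this trial.

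**The case against.** The strongest reply is that footnote 3 is the usual convention, loosely worded: history closes at screening, and anything medically significant that happens afterwards goes on the AE page. The layout of Table 1 and the consent start date in footnote 9 both fit that reading. It may well be what was meant. But it needs a condition that the sentence does not contain, and nothing else in the protocol or SAP supplies one.

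A reader might also infer that footnote 1 leaves sites with a stale history. Study days 85 and 169 for Cycles 4 and 7 imply 28-day cycles, so six parent cycles would make the reused history at least 6 × 28 = 168 days old. The documents do not support that. Footnote 1 allows reuse for eligibility only and does not say which parent-study assessment is used. Section 6.2.3 and footnote 3 still require a history that covers past Tenalisib and the last four weeks of medication, which a history taken at parent-study baseline could not contain. The parent cycle length is not given either.

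Another tempting inference is that related AEs must be inflated, because Section 7.2 says "All toxicities should be considered to be related to Tenalisib unless there is a clear alternative explanation". The same section classes an event as not related when there is no temporal association or another cause is identified. A carried-over Tenalisib toxicity could still be called related, but this is a possibility for some entries and not a necessary result.

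Finally, the error can run the other way: a toxicity ongoing at rollover may be filed only as history and, with no worsening rule, not counted if it gets worse. This point stands, and it also argues for an explicit onset-or-worsening rule.

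**Conclusion.** The concern holds as a defect of a stated rule. Followed literally, footnote 3 turns a condition that predates consent into an AE of this study when it is first noted later, and nothing downstream removes it. AE incidence and individual event terms can be inflated. The amount cannot be estimated from the documents beyond 2 points per misclassified patient on an event term, at about 50 patients, and on overall incidence only where that patient has no other AE.

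Two larger claims should not be made. One is to assume that 10% to 30% of entrants (5 to 15 of 50) are affected and read this as 10 to 30 points of overall incidence. The share has no basis in the documents, and the conversion requires that none of those patients has any other AE. The other is to call AE incidence the main endpoint. Protocol Section 3.1 lists AEs and date of progression without ranking them, and Section 9 gives continued access as the primary purpose.

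The study is single-arm and descriptive with no hypothesis test, so no formal inference is affected. The conclusion rests on sites following the footnote as written and on some pre-existing conditions not being listed at screening.

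**What to change.** 1. Reword Table 1 footnote 3 along these lines: a medical condition with onset, or worsening in grade, after informed consent is recorded as an AE; a condition that began earlier and is first noted at a later visit is added to medical history with its onset date and grade.
2. At entry, list the conditions and AEs ongoing at the end of the parent study, with their grade, from existing parent-study records. This gives the reference for judging worsening and keeps carried-over toxicities visible without counting them as new.
3. In the SAP safety section, apply the same onset-or-worsening rule to the AE counts.

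The cost is a reworded footnote, a matching sentence in the SAP, and a small amount of extra history transcription at the sites. No additional visits or tests are needed.
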